3.4 Exclusion Criteria

- End Stage Renal Failure and on Renal Replacement Therapy (HD, PD or Renal Transplant)

3.5 Withdrawal Criteria

Not applicable

3.6 Study Outcomes

1. Incidence of Hospital-acquired AKI at our centre during study period
2. Renal recovery at 90 days after AKI diagnosis
Definition for renal recovery:
 - a. Full recovery: Return of serum creatinine to or below baseline or within 20% of baseline creatinine
 - b. Partial recovery: Serum creatinine remaining 20% above the baseline, but below 50% of the baseline and not dialysis dependent or if previously requiring dialysis and now is dialysis Independent.
 - c. Failure to recover: Serum creatinine remains 50% above the baseline or dialysis dependent.
3. In-hospital mortality (from date of AKI diagnosis until date of death in hospital)

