Specific Objectives	
• To determine the incidence pattern of Hospital-acquired Acute Kidney Injury in Hospital Selayang• To study the determinants associated with development of Hospital-acquired Acute Kidney Injury in Hospital Selayang• To describe the survival outcomes of admissions with Hospital-acquired Acute Kidney Injury, admissions with Community-acquired Acute Kidney Injury and admissions without Acute Kidney Injury in Hospital Selayang
Study endpoints/outcomes	Completion of data collection at the end of the study duration
Sample Size	170000 (minimum 11345 required)
Study Duration	1 year

1. Background and Significance

Acute kidney injury (AKI) is a common problem globally which imposed heavy illness burden to the healthcare system, especially in developing countries. (1, 2) AKI can occur in the community (termed as Community-acquired AKI (CA-AKI)) or in the hospital setting (termed as Hospital-acquired AKI (HA-AKI)). Studies have associated HA-AKI as a preventable disorder, and linked HA-AKI with several immediate and long-term outcomes adversely, such as length of hospitalization, morbidity, and residual renal function. (1, 3, 4) Moreover, delayed recovery to baseline kidney function after AKI episode is found to be associated with higher risk of adverse events and mortality. (5) The impact of HA-AKI is significantly profound, especially among HA-AKI survivors who lost their residual renal function, and remain dialysis dependent. (6)

There was an increasing trend in HA-AKI incidence among hospitalized patients.(6-8) This could be attributed to increased exposure to potentially preventable risk factors during hospitalization. (6) However, studies pertaining to Asian countries are scarce, especially Malaysia. Preventative strategies against HA-AKI could be formulated based on understanding of risk factors which could be identified earlier upon hospital admission. (4)

The purpose of this study is to compare the incidence trend of HA-AKI in Selayang Hospital for the past 15 years, as well as to determine characteristics predictive of such cases. Understanding of clinical variables associated with HA-AKI could facilitate strategies and approaches to prevent, recognize HA-AKI early and mitigate the disease burden of HA-AKI in future.

2. Objective

2.1 *General Objective*

To investigate the incidence, characteristics and outcomes of Hospital-acquired Acute Kidney Injury in Hospital Selayang over 15 years

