3.3 Inclusion Criteria

- a) Age of 18 and above at time of hospital admission
- b) HA-AKI is defined by any patient who developed AKI (as per definition below) after 48 hours of hospital admission.
- c) Definition of AKI(9):

- i. An increase in serum creatinine of 0.3 mg/dl (26.5 μ mol/l) within 48 hours *OR*
- ii. An increase in serum creatinine to more or equal to 1.5 times baseline, which is known or presumed to have occurred within the prior 7 days

d) Definition for baseline creatinine(9):

- i. The baseline creatinine level is defined as the creatinine level at or within 7 days before the hospital admission, *OR*
 - ii. at the hospital admission *OR*
 - iii. the lowest creatinine (excluding the post dialysis creatinine if dialysis is initiated) during the index hospitalisation for those whose baseline creatinine were unknown.

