3.7 Sample Size

The primary outcome of interest is development of HA-AKI during admission at our centre. The incidence of Hospital-acquired AKI at our centre at March 2017 was 1.19% based on one ongoing study (A prospective, multicenter, observational study to determine the incidence and outcome of Acute Kidney Injury among hospitalised patients in Malaysia). The nine variables to be investigated for predictors of HA-AKI are age, gender, ICU

admission, race, nephrotoxin use, diabetes mellitus, hypertension, congestive heart failure and chronic obstructive pulmonary disease. With an estimation of 15 events per predictor, a minimum of 135 events would be needed, translating to a minimal of 11345 patients at our centre required for the study. The study population fits the minimum sample size requirement as 170283 adult admissions were recorded in total (22788 for Year 2002, 41731 for Year 2007, 46330 for Year 2012 and 59434 for Year 2017).

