3.10 Statistical Analysis Plan

The analyses will be performed using IBM SPSS Statistics for Windows (Version 23.0. Armonk, NY: IBM Corp.). Descriptive statistics will be utilized for selected variables. The results will be presented as frequencies and percentage for Categorical Data. Numerical Data which is normally distributed will be presented as mean and standard deviation while median and interquartile range will be presented for Numerical Data which is not normally distributed.

Comparing Numerical Data which is normally distributed between two groups will be analysed using the Independent t-test while Mann-Whitney test will be used if not normally distributed. Multiple logistic regression will be used to study association between risk factors (Numerical Data/Categorical Data) and outcome (Categorical Data). The survival analyses and survival curves from the date of diagnosis until death will be performed using the Kaplan-Meier method, to estimate the index hospitalisation survival rate. All probability values will be two-sided and a level of significance of less than 0.05 (p-value < 0.05) will be considered as statistically significant.

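### The 15-year HA-AKI trend is measured per admission with no length-of-stay or patient-day measure, so it could not separate a change in daily risk from a change in days observed

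*Combined protocol and SAP*

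**What the plan says.** The Background (section 1) gives the purpose as to "compare the incidence trend of HA-AKI in Selayang Hospital for the past 15 years", and to find characteristics that predict HA-AKI. Section 3.6 lists "Incidence of Hospital-acquired AKI at our centre during study period" with no denominator or time unit. Section 3.7 makes the outcome binary and per stay: "The primary outcome of interest is development of HA-AKI during admission at our centre". Section 3.3 sets when risk begins but not when it ends: "HA-AKI is defined by any patient who developed AKI (as per definition below) after 48 hours of hospital admission".

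For determinants, section 3.10 states: "Multiple logistic regression will be used to study association between risk factors". Section 3.7 names nine predictors; beyond age, gender and ICU admission they are "race, nephrotoxin use, diabetes mellitus, hypertension, congestive heart failure and chronic obstructive pulmonary disease". Length of stay, days at risk and calendar window are not among them.

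The only time-to-event method in section 3.10 is Kaplan-Meier from diagnosis to death, which starts after the event at issue here. Length of hospitalisation appears only in the Background, as an outcome linked to HA-AKI.

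**The concern.** Over an open-ended stay, the chance of HA-AKI depends on the daily risk after hour 48 and on how many days the patient remains in hospital to be observed. A per-admission proportion combines the two. Within one window that does no harm to a statement of burden. Across windows 15 years apart, a shorter average stay could hide a rising daily risk, and a longer one could imitate it. Nothing the plan reports would let a reader tell these apart.

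The Background wants the trend to inform prevention, and the response differs according to whether daily risk or time in hospital has changed. The windows are also large, so even a modest difference in stay could give a statistically significant trend.

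**Working it through.** **The plan's own figure.** Section 3.7 uses nine predictors, 15 events each and an incidence of 1.19%: 9 × 15 = 135 events, and 135 / 0.0119 = 11,344.5, rounded up to 11,345. This reproduces. The window counts 22,788 + 41,731 + 46,330 + 59,434 sum to 170,283, as stated. This point changes neither figure.

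**Inputs for the illustration.** From section 3.7: 1.19% (March 2017), 22,788 admissions for 2002 and 59,434 for 2017. Assumed, because the documents give no stay: a 2017 mean stay L of 3, 4 or 5 days, exponentially distributed, and a constant daily hazard h after day 2, the same in both years. The 1.19% is taken to be per adult admission; its denominator is not stated.

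**Formula.** Risk per admission = exp(−2/L) × h / (h + 1/L). The first factor is the share still in hospital at 48 hours; the second is the chance that HA-AKI comes before the end of the stay.

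**Worked case, L = 4 in 2017.**
- Share beyond 48 hours: exp(−0.5) = 0.6065. Solving 0.6065 × h / (h + 0.25) = 0.0119 gives h = 0.00500, or 5.0 per 1,000 at-risk days.
- 2002 with a 25% longer stay, L = 5: exp(−0.4) × 0.00500 / 0.20500 = 0.6703 × 0.02441 = 1.64%.
- Apparent odds ratio, 2017 vs 2002: (0.0119 / 0.9881) / (0.01636 / 0.98364) = 0.72, although h is identical.

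**Across the assumed 2017 stays of 3, 4 and 5 days** (h = 7.9, 5.0 and 3.6 per 1,000 at-risk days):

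| 2002 mean stay relative to 2017 | 2002 incidence (2017: 1.19%) | Apparent OR, 2017 vs 2002 | Approximate chance of p < 0.05 |
|---|---|---|---|
| 25% longer | 1.60% to 1.69% | 0.70 to 0.74 | 99% or more |
| 10% longer | 1.36% to 1.39% | 0.86 to 0.88 | about one half to 60% |
| 20% shorter | 0.81% to 0.86% | 1.38 to 1.48 | about 99% |

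In every row the rate per at-risk day is the same in both years (ratio 1.00).

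**Counting only stays beyond 48 hours.** Part of the effect above comes from the share of admissions that reach 48 hours. Without that factor, the risk is hL / (1 + hL) and its odds are hL. The apparent odds ratio is then simply the ratio of mean stays: 1 / 1.25 = 0.80. For L = 4 vs 5, the at-risk stays are 59,434 × 0.6065 ≈ 36,049 and 22,788 × 0.6703 ≈ 15,275, with risks of 1.96% and 2.44%. This gives z = 0.00478 / √(0.0244 × 0.9756 / 15,275 + 0.0196 × 0.9804 / 36,049) ≈ 3.3. The right denominator therefore shrinks the distortion but does not remove it.

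**The case against.** The strongest reply is that the probability of HA-AKI during a stay is a legitimate target. The protocol speaks of disease burden and of risk factors recognisable at admission, and it never claims to estimate a daily risk. That stands, and the per-admission figure should remain.

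The documents do not support four stronger readings.

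- **That stays did change.** Admissions rose 2.6-fold (59,434 / 22,788), and a reader might infer that stays changed with them. Admission counts identify neither the length of stay nor its direction of change. The illustration largely returns the assumption put into it: at a low constant hazard, risk is nearly proportional to days.
- **That discharged or deceased patients are misclassified.** HA-AKI is an in-hospital event by definition. A stay that ends without it is correctly a non-event, and the simple proportion is the cumulative incidence with discharge and death as competing events.
- **That the determinant odds ratios are wrong.** A longer stay is part of how a predictor raises per-admission risk. The odds ratios mislead only if read as effects on daily risk. Window is not a listed predictor, so the trend problem lies in the window-by-window comparison, not in the logistic model.
- **That the patient-day rate should decide which trends are real.** Crude rates shift with case mix. Suppose 80 of 100 admissions carry 2 per 1,000 days and 20 carry 6 per 1,000. Low-risk days at risk fall from 4 to 2 while high-risk days stay at 8. The rate goes from (0.64 + 0.96) / 480 = 3.3 to (0.32 + 0.96) / 320 = 4.0 per 1,000, a 20% rise with nobody's daily hazard changed.

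**Conclusion.** The point holds in a limited form. The plan compares a per-admission yes/no outcome over an open-ended risk period across four windows and includes nothing that would show whether days at risk changed. A trend in that proportion could be reported as burden but could not be read as a change in daily risk.

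The size and direction of any distortion are unknown. The apparent odds ratio of 0.70 to 0.74 (0.80 among stays beyond 48 hours) rests on an assumed 25% difference in mean stay, exponential stays, a constant hazard and a per-admission reading of the 1.19%. It shows what a difference in stay could do, not what happened at this hospital. The change is a cheap improvement to interpretation; the planned primary analysis is not invalid without it.

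**What to change.** In sections 3.6 and 3.10:

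1. Keep the per-admission proportion for each window and state its denominator.
2. For each window, also report length of stay and HA-AKI per 1,000 at-risk patient-days. Count days from hour 48 to AKI onset, discharge or death, among admissions still in hospital and AKI-free at 48 hours.
3. Compare windows with a Poisson model that has period as a factor and log at-risk days as the offset. Adjust for age and other admission characteristics, because crude rates also move with case mix.
4. State that a per-admission trend will be interpreted as a change in daily risk only with reference to these results, without a pass/fail rule.
5. Make any time-at-risk version of the determinants model a sensitivity analysis. Date ICU admission and nephrotoxin use and treat them as time-varying, since coding them as ever/never would introduce immortal-time bias. Do not adjust for total length of stay, which HA-AKI can itself prolong.

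The cost is SAP wording, some data preparation and two incidence measures to explain. Admission and discharge times are needed for all at-risk stays. Section 3.1 mentions retrieving only creatinine results from the Laboratory Information System, so the investigators should confirm that these times can be extracted. Dated exposures for item 5 would be more work, which is another reason to keep it optional.

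### The percentage-only recovery classes in 3.6 do not match the absolute-rise AKI rule in 3.3, so an unchanged creatinine can be graded as partial or full recovery

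*Combined protocol and SAP*

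**What the plan says.** Section 3.3(c) gives two alternative ways to qualify as AKI. Rule (i) is "An increase in serum creatinine of 0.3 mg/dl", that is 26.5 µmol/l, within 48 hours. Rule (ii), with its window counted in days, is "An increase in serum creatinine to more or equal to 1.5 times baseline, which is known or presumed to have occurred within the prior 7". Rule (i) carries no minimum percentage and is not tied to baseline. Baseline itself is set in 3.3(d), whose first option reads "The baseline creatinine level is defined as the creatinine level at or within 7 days before the hospital admission"; the fallbacks are the admission value and then the lowest value of the stay.

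Section 3.6 lists "Renal recovery at 90 days after AKI diagnosis" as the second outcome, in three classes:
- "Full recovery: Return of serum creatinine to or below baseline or within 20% of baseline creatinine"
- "Partial recovery: Serum creatinine remaining 20% above the baseline, but below 50% of the baseline and not dialysis dependent"; a patient who was dialysed and has come off dialysis is also placed here
- "Failure to recover: Serum creatinine remains 50% above the baseline or dialysis dependent"

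No class refers to the rule by which the patient entered, and none requires a fall from the AKI peak. Section 3.4 excludes only end-stage renal failure on replacement therapy, so patients with a high baseline who are not on replacement therapy stay in. Section 3.10 does not mention renal recovery and does not say whether partial recovery counts as recovered.

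**The concern.** Entry can be on an absolute scale, but outcome is always on a relative one. Someone who entered on rule (i) alone may never have been 50% above baseline. For that patient the scale cannot separate a creatinine that returned from one that stayed at its peak unless the peak was more than 20% above baseline, and even then the unchanged value is called partial recovery.

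Two things are at stake. Within a period, the combined full and partial proportion can look better than the course of creatinine warrants. Across periods, the Research Synopsis frames the study as a 5-yearly trend over 15 years that includes outcomes. If the share of cases entering on rule (i) alone differs between the four periods, the recovery distribution can move without any change in prognosis.

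**Working it through.** The plan gives no computed figure for recovery. Its one computed design figure, the minimum sample size in 3.7, reproduces (9 × 15 = 135 events; 135 / 0.0119 = 11,344.5, rounded up to 11,345) and does not depend on this point.

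**Inputs.** Rule (i) rise of 26.5 µmol/l and rule (ii) ratio of 1.5 (3.3); cut-offs of 20% and 50% above baseline (3.6). The partial class is read as above 20% and below 50% over baseline, which is the plain intent. The patient is not dialysed and has a day-90 value.

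**Step 1: thresholds.** Let B be baseline and let the rise start from B.
- The minimum rise equals 50% of B at B = 26.5 / 0.50 = 53 µmol/l. At or below this, a rule (i) rise also meets rule (ii).
- The minimum rise equals 20% of B at B = 26.5 / 0.20 = 132.5 µmol/l.

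**Step 2: grade if creatinine stays at peak, for a rise of exactly 26.5 µmol/l.**

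| Baseline (µmol/l) | Peak | Above baseline | Entry rule met | Grade if unchanged at day 90 |
|---|---|---|---|---|
| 45 | 71.5 | 58.9% | (i) and (ii) | failure |
| 60 | 86.5 | 44.2% | (i) only | partial |
| 80 | 106.5 | 33.1% | (i) only | partial |
| 120 | 146.5 | 22.1% | (i) only | partial |
| 150 | 176.5 | 17.7% | (i) only | full |
| 200 | 226.5 | 13.2% | (i) only | full |

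**Step 3: larger rises.** A patient below 1.5 × B has a rise below 0.5 × B. The unchanged value is full if the rise is at most 0.2 × B and partial otherwise.
- B = 140: full for rises of 26.5 to 28, partial from there to just under 70.
- B = 200: full for rises of 26.5 to 40, partial from there to just under 100.

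So at baselines of 132.5 or more, full at peak applies to the smaller rises only.

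**Step 4: rises that start below baseline.** Admission baseline 120, in-hospital low 85, then 115 within 48 hours. The rise is 30, so rule (i) is met, yet the peak is below baseline and is graded full. Likewise 100, then 80, then 107: rise 27, 7% above baseline, full.

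**Step 5: exceptions.** Baseline 100, slow drift to 135 on day 8 and 162 on day 10. The 48-hour rise is 27, so rule (i) is met. The ratio is 1.62, but it took more than 7 days to reach, so rule (ii) is not clearly met. This patient is at failure level at peak. Later worsening or dialysis dependence also gives failure.

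**Step 6: size.** Let q be the share of assessed cases that enter on rule (i) alone and stay below 1.5 × B, and u the share of those still at peak level at day 90. The overstatement of full plus partial is q × u. The documents give neither. Assuming q of 10–70% and u of 10–50%, the product runs from 0.10 × 0.10 = 1 point to 0.70 × 0.50 = 35 points. That is a range of assumptions, not an estimate. For the trend: with u held at 30%, a change in q from 30% to 50% moves the overstatement from 9 to 15 points, a 6-point apparent gain with no change in the true proportion unrecovered.

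**The case against.** The strongest reply is that 3.6 grades function at day 90 against baseline, not the fall from peak. On that view a value 20–50% above baseline is a modest residual deficit and *partial* describes it fairly, while a value below the plan's own baseline is reasonably called full. A patient whose creatinine did come down is labelled correctly whichever rule admitted them. The plan also defines no pooled recovery rate, and renal recovery appears in neither the specific objectives (2.2) nor the analysis plan (3.10).

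Much of this stands, and it rules out three stronger conclusions that a reader might draw:
- *The recovery rate is overstated.* The documents support only that it can be. Just the patients still raised at day 90 are affected, and nothing is given on how many there are. If recovery means full only, the effect is essentially confined to smaller rises at baselines of 132.5 µmol/l or more and to rises starting below baseline.
- *Patients entering on rule (i) alone can never be failures.* They can, through later worsening, dialysis dependence or a slow rise.
- *Such patients are graded as recovered at diagnosis.* The grade is given at 90 days.

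What the reply does not remove is the mismatch itself. The same class holds patients who improved and patients who did not, how far this happens depends on the entry rule and baseline, and no other section separates them.

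**Conclusion.** The mismatch between 3.3(c)(i) and 3.6(2) is real and follows from the plan's own cut-offs. For non-dialysed patients with a day-90 value who entered on rule (i) alone and stayed below 1.5 times baseline, an unchanged creatinine is graded partial or full, with the dividing lines at 53 and 132.5 µmol/l for the minimum rise measured from baseline.

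The effect is a possible upward bias in full plus partial recovery and a possible spurious trend across the four periods. Its size cannot be computed, because the documents give no baseline creatinine distribution, no share entering on rule (i) alone and no day-90 data. The concern is limited to one outcome and warrants an inexpensive improvement to reporting.

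**What to change.** Keep the three classes in 3.6(2) and add to 3.6 and 3.10:
- Report full, partial and failure separately; do not pool full and partial.
- Tabulate them in each of the four periods for patients meeting rule (ii) (including those meeting both rules) and for patients meeting rule (i) only, stating in advance where a rise to 1.5 times baseline over more than 7 days belongs.
- Within this, split by baseline creatinine, below versus at or above 132.5 µmol/l.
- Base any statement about the trend in recovery on the rule (ii) stratum, with the rule (i)-only stratum shown alongside.

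Redefining recovery by the fall from peak is tempting but makes new errors. Suppose full recovery also required less than 26.5 µmol/l above the value where the rise began, and failure included no fall from peak. Baseline 140, peak 166.5 and day-90 value 166 would still be full (26.0 µmol/l and 18.6% above baseline) after a fall of 0.5. The 120, 85, 115 patient with a day-90 value of 118 would become a failure while below baseline.

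The cost is a few lines of wording, extra tables and smaller strata, and the trend statement would cover only part of the cases. Entry rule and baseline come from creatinine values that 3.1 already retrieves. Day-90 values are needed for this outcome in any case; the documents do not confirm that post-discharge values are in that extract, so the tables cover only patients who have one.

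### The creatinine limits for partial renal recovery in 3.6 cannot both be met, so never-dialysed patients between 120% and 150% of baseline have no recovery class

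*Combined protocol and SAP*

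**What the plan says.** Section 3.6 (Study Outcomes) lists as outcome 2 "Renal recovery at 90 days after AKI diagnosis" and sorts patients into three classes.

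- Full recovery (2a): "Return of serum creatinine to or below baseline or within 20% of baseline creatinine".
- Partial recovery (2b): "Serum creatinine remaining 20% above the baseline, but below 50% of the baseline", in a patient who does not depend on dialysis. A second route follows: "or if previously requiring dialysis and now is dialysis Independent".
- Failure to recover (2c): "Serum creatinine remains 50% above the baseline or dialysis dependent".

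This is the only definition of recovery in the document. Section 3.10 (Statistical Analysis Plan) does not mention renal recovery, and nothing elsewhere restates the limits.

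**The concern.** The upper limit in 2b is written as a level (half of baseline), whereas the lower limit in 2b and the limit in 2c are written as rises above baseline. A level under half of baseline cannot coexist with a rise of 20%. It would also already count as full recovery under 2a, being below baseline.

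The range left uncovered is the one that partial recovery should describe. If the rule is coded as it stands, never-dialysed patients in that range are left blank. Partial recovery then changes its meaning, from incomplete return of creatinine to having come off dialysis. If the rule is repaired informally, the result depends on who repairs it. Section 3.1 has data collectors gathering the data, and the document does not say who assigns the recovery class. Two people working from the same text could therefore report different recovery distributions.

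**Working it through.** **Inputs.** All limits come from 3.6. Let r be serum creatinine at 90 days divided by baseline. I read 20% above in 2b as more than 20% above, and 50% above in 2c as 50% or more above, so that r = 1.2 belongs to 2a and r = 1.5 to 2c.

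**The plan's own figure.** The recovery definition carries no computed figure. The only one in the document is the minimum sample size in 3.7: "With an estimation of 15 events per predictor, a minimum of 135 events would be needed", at an incidence of 1.19%. Nine predictors × 15 = 135 events, and 135 / 0.0119 = 11,344.5, which rounds up to 11,345 as stated. No recovery limit enters this calculation.

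**Limits as written.**

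- 2a: r ≤ 1.2.
- 2b, creatinine limb: r > 1.2 and r < 0.5, without dialysis dependence. No value of r satisfies both. With a baseline of 100 µmol/l, creatinine would have to be above 120 and below 50.
- 2b, dialysis limb: previously dialysed and now independent. Read as a separate alternative, it has no creatinine limit.
- 2c: r ≥ 1.5, or dialysis dependent.

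**Classification by dialysis status, as written.** The rules were applied over r from 0.1 to 4.0 in steps of 0.001.

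| Patient | r ≤ 1.2 | 1.2 < r < 1.5 | r ≥ 1.5 |
|---|---|---|---|
| Never dialysed | full | none | failure |
| Previously dialysed, now independent | full and partial | partial | partial and failure |
| Dialysis dependent | full and failure | failure | failure |

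On this grid, never-dialysed patients had no class from r = 1.201 to r = 1.499. No previously dialysed, now independent patient was without a class.

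**With the upper limit read as less than 50% above baseline (r < 1.5).** Only one cell changes: never-dialysed patients with 1.2 < r < 1.5 become partial. Their three classes then have no gap and no overlap. The double entries in the other two rows remain.

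**Scale, for illustration only.** The document gives no share of patients in the range, so the share is an assumption. If the 1.19% incidence applied to all 170,283 admissions in 3.7, there would be 170,283 × 0.0119 ≈ 2,026 cases of hospital-acquired AKI. If 5%, 10% or 20% of them were never dialysed and in the range, about 101, 203 or 405 patients would have no class. The 1.19% refers to March 2017 only. Deaths and missing 90-day creatinine would reduce the number who can be classified.

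**The case against.** The strongest reply is that nobody would apply the rule literally. Class 2a already uses a percentage of baseline to mean a distance from it, 2b opens with a rise of 20%, and 2c starts at a rise of 50%. Three ordered classes leave one sensible reading, and a patient between the outer two would most naturally be called partial. This stands as to intent, and it is why the correction is safe: it brings in no threshold from outside the document. It does not make the text usable as a rule. In 2a the word within carries the sense of distance, and 2b has no such word.

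A reader might infer that the partial class is empty and that everyone 20% to 50% above baseline is unclassified. The document does not support that. The dialysis clause, read naturally as an alternative, admits previously dialysed patients who are now independent, whatever their creatinine. The class would be empty only if that clause were nested under the creatinine condition. It would then be redundant, because such patients already do not depend on dialysis.

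It is also fair to say that little else in the plan rests on this phrase. Section 3.7 names development of hospital-acquired AKI as the primary outcome, and the specific objectives in 2.2 cover incidence, determinants and survival. Recovery is nevertheless a listed outcome, and the general objective in 2.1 covers outcomes.

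**Conclusion.** The creatinine limb of 2b is wrong as written. Its two limits exclude each other, and never-dialysed patients above 120% and below 150% of baseline have no recovery class. Literally applied, partial recovery is confined to patients who were dialysed and are now independent.

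The practical harm is limited. The intent can be recovered from 2a and 2c, and misclassification follows only if the rule is coded literally or repaired inconsistently. A reader might conclude that the recovery results will necessarily be wrong, or that the main findings are at risk. Neither follows: the incidence of hospital-acquired AKI and the minimum of 11,345 patients are unaffected. The number of patients concerned cannot be derived from the document.

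The conclusion rests on two readings: that the dialysis clause in 2b is a separate alternative, and that values exactly at the limits go to 2a and 2c. The second affects only patients exactly at 120% or 150%.

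**What to change.** In 3.6, outcome 2b, replace the upper limit by the statement that creatinine is less than 50% above baseline. The creatinine bands then agree with 2a and 2c: up to 120%, above 120% to below 150%, and 150% or more of baseline.

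This closes the gap for never-dialysed patients only. The same edit should state how dialysis status ranks against creatinine, because two overlaps remain:

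- Previously dialysed, now independent patients also meet 2a at or below 120% and 2c at or above 150%.
- Dialysis-dependent patients at or below 120% meet both 2a and 2c, because 2a carries no dialysis condition.

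The investigators should choose the ranking and write it down before recovery is classified. The cost is one phrase and one sentence in 3.6, with the same wording in any data sheet or code that assigns the class. No new data are needed, and the sample size does not change.

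### The 90-day renal recovery classes overlap for patients who had dialysis, and the partial-recovery creatinine band is misworded

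*Combined protocol and SAP*

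**What the plan says.** Section 3.6 lists renal recovery 90 days after AKI diagnosis as the second of three outcomes and defines three classes:

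- Class a: "Full recovery: Return of serum creatinine to or below baseline or within 20% of baseline creatinine".
- Class b: "Partial recovery: Serum creatinine remaining 20% above the baseline, but below 50% of the baseline and not dialysis dependent or if previously requiring dialysis", where the final condition continues to patients who have since come off dialysis ("or if previously requiring dialysis and now is dialysis Independent").
- Class c: "Failure to recover: Serum creatinine remains 50% above the baseline or dialysis dependent".

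Neither section 3.6 nor the Statistical Analysis Plan (section 3.10) says which class prevails when a patient meets two. Section 3.10 names no analysis of recovery.

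Section 3.4 excludes "End Stage Renal Failure and on Renal Replacement Therapy (HD, PD or Renal Transplant"). That removes patients already on replacement therapy for end-stage disease. It does not remove those who start dialysis for the AKI episode.

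**The concern.** A set of outcome classes should give each patient exactly one label. Here the best and the worst class are defined on different variables: class a looks only at creatinine, whereas class c can be reached through dialysis status alone. Two people applying the text carefully could code the same dialysed patient differently. Section 3.1 gives data collection to data collectors, and the protocol does not say who assigns the recovery class.

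The patients caught by this are ones the protocol cares about. Section 1 describes the impact of HA-AKI as profound "especially among HA-AKI survivors who lost their residual renal function, and remain dialysis dependent". Recovery also falls under the general objective in section 2.1: "To investigate the incidence, characteristics and outcomes of Hospital-acquired Acute Kidney Injury in Hospital Selayang over 15 years". At stake is whether the recovery figures mean one definite thing, and mean the same thing in each of the four admission periods.

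**Working it through.** **The plan's own figure.** Section 3.7 asks for 15 events for each of 9 predictors: 15 × 9 = 135 events. At an incidence of 1.19%, 135 / 0.0119 = 11344.5, which rounds up to the stated 11345. The figure reproduces. It concerns development of HA-AKI only, and the recovery classes do not enter it.

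**Inputs for the class check.** These are the three definitions in section 3.6. Let r be the day-90 creatinine divided by baseline. Class b is first read as evidently intended, with r from 1.2 to below 1.5.

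- Class a holds if r ≤ 1.2, whatever the dialysis status.
- Class c holds if r ≥ 1.5, or if the patient is dialysis dependent at any r.
- Class b holds if r is in the band and the patient is not dialysis dependent. The clause on patients who have come off dialysis can be parsed in two ways: as a separate route into class b at any r, or as a further condition inside the band.

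| Patient at day 90 | r below 1.2 | r between 1.2 and 1.5 | r 1.5 or more |
|---|---|---|---|
| Never dialysed | full | partial | failure |
| Weaned, clause is a separate route | full and partial | partial | partial and failure |
| Weaned, band governs the clause | full | partial | failure |
| Dialysis dependent, either parsing | full and failure | failure | failure |

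**Step 1, dialysis dependent.** At r = 1.1, for example, class a is met because 1.1 ≤ 1.2, and class c is met because of dialysis. The parsing of class b makes no difference, so this overlap is present on every reading.

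**Step 2, weaned.** If the clause is a separate route, r = 1.1 meets classes a and b, and r = 1.8 meets classes b and c. If the band governs, r = 1.1 is full only and r = 1.8 is failure only. The text does not settle which parsing applies.

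**Step 3, the boundary.** At exactly r = 1.2, a patient not on dialysis can be read both as within 20% of baseline and as remaining 20% above it. This is a minor drafting gap.

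**Step 4, the literal band.** A value below 50% of baseline means r < 0.5. A value 20% above baseline means r of at least 1.2. No r satisfies both, so nobody can enter class b through creatinine. A never-dialysed patient at r = 1.35 would then have no class. Reading the phrase as less than 50% above baseline removes the contradiction.

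**Step 5, does another section resolve it?** Section 3.3 sets aside post-dialysis creatinine, but only where baseline is taken as the lowest in-hospital value. No such rule is stated for the day-90 value. Section 3.10 is silent on recovery.

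**The case against.** The strongest reply is that sensible coders would not be misled. A return of creatinine most naturally means recovered kidney function, not a value lowered by dialysis; class c names dialysis dependence without qualification; and section 3.3 shows that the investigators know dialysis distorts creatinine. On that view a dialysis-dependent patient is plainly a failure, the weaned-patient overlap disappears once the band governs the clause, and the 50% phrase is a typing slip. Much of this stands. Common sense probably does settle the dialysis-dependent case, and the slip is easily recognised. But the rule is unwritten, and common sense does not choose between the two parsings for weaned patients.

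A reader might infer more than the text supports in three ways.

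- That the double classing of weaned patients is certain. It is not; it depends on the parsing.
- That the number misclassified can be had by applying the 1.19% incidence to the admissions in section 3.7. That product would count HA-AKI cases, not dialysed patients, and would assume one incidence for four periods in a study of whether incidence changed.
- That deaths before day 90 and patients without a day-90 creatinine show the same fault. Section 3.6 indeed gives deaths before day 90 no recovery class, nor patients with no creatinine whose dialysis status does not decide it. But that is a separate omission, and the overlap neither causes it nor depends on it.

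**Conclusion.** The point holds for patients who had dialysis. The clash between full recovery and failure for dialysis-dependent patients at up to 1.2 times baseline is present on every reading. The clash for weaned patients, at up to 1.2 times and at 1.5 times or more, is present only if the clause is a separate route into partial recovery. The literal partial band is impossible to meet and needs correcting. Apart from the exact 20% boundary, never-dialysed patients fall in one class once that slip is corrected.

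The size in patients cannot be computed: the documents give neither a dialysis rate nor a distribution of day-90 creatinine. The consequence is limited. The primary outcome is development of HA-AKI, the sample size reproduces without reference to recovery, and no specific objective names recovery. A reader might conclude that the study's main results are in doubt; the documents do not support that. The correction is still worth making before recovery is coded, because the stated rules conflict for a listed outcome and the remedy costs almost nothing.

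**What to change.** In section 3.6:

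1. Add to full recovery that the patient is not dialysis dependent, so that it agrees with class c.
2. Reword partial recovery as creatinine more than 20% but less than 50% above baseline and not dialysis dependent.
3. Word failure as creatinine 50% or more above baseline, or dialysis dependent.
4. Have the investigators reconcile the weaned-from-dialysis clause with full recovery and failure through one stated precedence rule. Which rule to adopt is for them to decide.

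The first three changes give r ≤ 1.2, 1.2 < r < 1.5 and r ≥ 1.5 for patients not on dialysis, and failure for those dependent on it. With the fourth, each living patient with a measured creatinine has exactly one class.

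As an optional reporting addition, deaths before day 90 (where recorded) and patients with no determinable class could be shown as separate counts beside the three classes.

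The cost is protocol wording and one coding rule. The recovery proportion may look slightly less favourable.
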